3.2.1 Clinical Event Committee

The CEC will include at a minimum, 2 interventional cardiologists and 2 electrophysiologists. Physicians on the CEC will not participate in the study as investigators and when reviewing events will be blinded to any patient or site information. The purpose of the CEC is to adjudicate all clinical events. Specifically:

- Classify clinical events as either an Acute Coronary Syndrome (ACS) Event, a Precursor Event, or a Non Event. Non Events will be further classified as either a Transient Ischemic Event or a Non Ischemic Event. Review all deaths, and adverse events associated with diagnostic testing or procedures performed as a result of a Type I ST Episode Detection and determine relationship to system and/or procedure.
- Review all baseline surface ECGs to determine the presence or absence of any conduction abnormality.
- Review all complications and all cardiovascular related adverse events

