4.4 Analysis of Efficacy

4.4.1 Primary Efficacy Endpoint

The efficacy endpoint will be evaluated as the sensitivity of the ST Monitoring Feature to detect clinical events. Sensitivity of the ST Monitoring Feature to detect clinical events will be calculated as the number of True Positive events (as defined in section 3.2.3) divided by the total number of ACS clinical events.

$$\text{Sensitivity} = \frac{\text{\# of TP events}}{\text{Total number of ACS events}}$$

A clinical event is considered to be related to the onset of a Type I ST episode if the clinical event occurs within 72 hours after the onset of a Type I ST episode.

The hypothesis is formally expressed as follows:

H_0 : Sensitivity \leq 50%

H_a : Sensitivity $>$ 50%

The desired outcome is to demonstrate that the sensitivity of the ST Monitoring Feature is greater than 50%. The null hypothesis will be rejected at the 2.5% significance level if the lower bound of the 95% confidence interval for sensitivity is greater than 50%. The lower confidence bound will be calculated using the Wilson score interval method.

Patient Group

All enrolled patients who have a successful implant or system revision, complete the Baseline follow up visit and have the ST Monitoring Feature and Patient Notifier turned ON, and experience clinical events will be included in the evaluation of this study endpoint. Data collection towards the study endpoint will begin after the Baseline visit.

Further, the analysis population for the primary efficacy endpoint will be those subjects with the Fortify[®] ST (upgraded), Fortify Assura[®] ST and Ellipse[®] ST devices. The data from subjects with a Fortify[®] ST prior to being upgraded will not be included in this analysis.

Statistical Analysis Plan

Analysis

Primary Analysis

The expected sensitivity for ST Monitoring Feature will be estimated by the number of true positive events divided by the total number of ACS events.

The 95% confidence limits will be calculated for sensitivity using the Wilson score interval method⁷ for a binomial proportion. The null hypothesis will be rejected if the lower bound of the 95% confidence limit is greater than 50%.

Additional Analysis

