4.5 Overall sample size and data cut-off

[figure not shown]
The total number of patients required for enrollment in order to satisfy the primary endpoints and the secondary endpoint is driven by the sample size requirement to satisfy the primary efficacy endpoint. Thus the total sample size required for this study is 5,228.

Data collection for the purposes of the FDA market approval application will be considered to be complete when the primary safety endpoint data are available and at least 41 clinical events have occurred.

Following submission of the clinical data, patients will continue to be followed until closure of the study for providing long-term follow up on the Investigational Devices.

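### The primary efficacy rule's stated 2.5% level is nominal: it is 2.98% exactly if 41 ACS events are analysed, and 1.78% to 3.30% over 41 to 60 events

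*Protocol*

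**What the plan says.** Section 4.4.1 (same text in both documents) tests H0: sensitivity at most 50% against Ha: sensitivity above 50%. The estimate is the "number of true positive events divided by the total number of ACS events". The null is to be "rejected at the 2.5% significance level if the lower bound of the 95% confidence interval for sensitivity is greater than 50" per cent, and "The lower confidence bound will be calculated using the Wilson score interval method". The Primary Analysis paragraph applies that method "for a binomial proportion". No continuity correction or exact test is named for this endpoint in the readable text.

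Protocol section 4.5, and section 3.1 of both documents, end data collection for the market application once the primary safety data are available and "at least 41 clinical events have occurred". The efficacy sample-size text is redacted, so the planning sensitivity, the power and the derivation of 41 cannot be seen.

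**The concern.** The plan equates a Wilson lower limit above 50% with rejection at the 2.5% level. Wilson is a normal-approximation method. With about 40 events the number detected moves in whole steps, and each step changes the tail probability by one to two percentage points near the cut-off, so the rule's true level can fall on either side of 2.5%.

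This is the only primary efficacy test and it may rest on few events. At the plan's minimum count, a borderline result of 27 out of 41 would be declared significant at 2.5% with an exact one-sided p-value of 0.030. Anyone checking a market application would find that quickly, and nothing in the readable text prepares for it.

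**Working it through.** **Inputs.** Null value 0.50, two-sided 95% Wilson interval (z = 1.96) and binomial model: section 4.4.1. Minimum count 41: Protocol section 4.5 and section 3.1 of both documents. Assumed here: all 41 are ACS events, and they are independent.

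**Where 2.5% comes from.** The Wilson lower limit exceeds 0.5 exactly when (x − n/2) / (√n / 2) > 1.96. The normal tail beyond 1.96 is 2.5%. That reproduces the plan's figure, as a normal approximation.

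**Cut-off at n = 41.** The condition is x > 20.5 + 1.96 × 6.403 / 2 = 26.77, so x must be at least 27. Wilson lower limits confirm it:
- 26/41: 0.4812, fail
- 27/41: 0.5055, pass

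**Exact level at n = 41.** P(X ≥ 27 | n = 41, p = 0.5) = Σ C(41, k) / 2^41 for k = 27 to 41 = 65,513,177,704 / 2,199,023,255,552 = 0.0298, i.e. 2.98%. The exact (Clopper-Pearson) 95% lower limit for 27/41 is 0.494, below 0.50. One more detection gives P(X ≥ 28) = 0.0138.

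**Other final counts.** The same two steps for each n:

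| ACS events | Wilson cut-off | Exact level | ACS events | Wilson cut-off | Exact level |
|---|---|---|---|---|---|
| 41 | 27 | 2.98% | 51 | 33 | 2.44% |
| 42 | 28 | 2.18% | 52 | 34 | 1.82% |
| 43 | 28 | 3.30% | 53 | 34 | 2.67% |
| 44 | 29 | 2.44% | 54 | 35 | 2.01% |
| 45 | 30 | 1.78% | 55 | 35 | 2.90% |
| 46 | 30 | 2.70% | 56 | 36 | 2.20% |
| 47 | 31 | 2.00% | 57 | 36 | 3.14% |
| 48 | 31 | 2.97% | 58 | 37 | 2.40% |
| 49 | 32 | 2.22% | 59 | 38 | 1.82% |
| 50 | 32 | 3.25% | 60 | 38 | 2.60% |

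Nine of the 20 counts exceed 2.5% (41, 43, 46, 48, 50, 53, 55, 57, 60). The range is 1.78% to 3.30% and the unweighted mean is 2.49%.

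**Price of an exact decision rule at 41 events.** An exact 2.5% test needs at least 28/41 (level 1.38%). The planning sensitivity is redacted, so these values are assumptions:

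| Assumed sensitivity | Power, ≥ 27/41 (Wilson) | Power, ≥ 28/41 (exact) |
|---|---|---|
| 0.65 | 52.6% | 39.7% |
| 0.70 | 77.6% | 66.5% |
| 0.75 | 93.3% | 87.8% |

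**The case against.** The strongest reply is that nothing has been miscalculated. Null, interval, confidence level and rule are all pre-specified, and a significance level paired with a score interval is ordinarily read as nominal. Any non-randomised test on a count has a level that jumps around its target, and averaged over 41 to 60 events this one sits at 2.49%. That stands. It means the rule need not change, but it does not make 2.5% the level delivered at a given count.

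Second, 41 is a floor, and it is worded as clinical events. Section 3.2.1 has the committee "Classify clinical events as either an Acute Coronary Syndrome (ACS) Event, a Precursor Event, or a Non Event", whereas the denominator of sensitivity is ACS events only. The number analysed may therefore be above or below 41. This also stands, so 2.98% must be stated as conditional. A reader might infer that the trial runs at a type I error of 2.98%, or that its error is inflated overall. The documents support neither: the final count is not fixed, and 11 of the 20 counts examined are below 2.5%.

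Third, a reader might infer that the plan is wrong unless it adopts an exact test. The plan does use exact methods elsewhere (the Poisson limit in section 4.3.3; Clopper-Pearson in section 4.3.1 when no complications occur), but it nowhere promises guaranteed exact size for sensitivity. At 41 events the exact rule undershoots 2.5% by 1.12 points, while Wilson overshoots by 0.48. Choosing between them is a trade-off.

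Fourth, raising the minimum to 42, where both rules need 28, might look like a cure. It is not: with 43 events the Wilson level is 3.30%.

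Finally, the redacted sample-size text could state an exact level. That cannot be checked.

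**Conclusion.** The point holds as a minor correction to a stated level. The plan's 2.5% should be read as nominal. If exactly 41 independent ACS events are analysed, the level is 2.98%, an excess of about half a percentage point; at other counts up to 60 it lies between 1.78% and 3.30%. The practical effect at 41 events is confined to one outcome, 27 detections, where the Wilson rule succeeds and an exact 2.5% test does not.

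The figures assume the uncorrected Wilson interval and independent events. Repeated ACS events within a patient would break independence; the patient-level bootstrap listed as an additional analysis in section 4.4.1 addresses that, but it is not the decision rule.

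**What to change.** In section 4.4.1 of both documents, replace the reference to the 2.5% significance level with: *at a nominal 2.5% level (exact level 3.0% at 41 ACS events; 1.8% to 3.3% over 41 to 60)*. Add that the exact one-sided binomial p-value, and the exact level of the Wilson rule at the final number of ACS events, will be reported alongside the Wilson bound.

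This changes neither the success rule nor the sample size. Its cost is a slightly less favourable stated level.

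The sponsor may instead make the exact binomial test the decision rule. That keeps the level at or below 2.5% at every count under the independence assumption, but loses about 6 to 13 points of power at 41 events over assumed sensitivities of 0.65 to 0.75, so power should be rechecked against the redacted planning value first.

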4.5 Overall sample size and data cut-off

[figure not shown]
The total number of patients required for enrollment in order to satisfy the primary endpoints and the secondary endpoint is driven by the sample size requirement to satisfy the primary efficacy endpoint. Thus the total sample size required for this study is 5,228.

Data collection for the purposes of the FDA market approval application will be considered to be complete when the primary safety endpoint data are available and at least 41 clinical events have occurred.

Following submission of the clinical data, patients will continue to be followed until closure of the study for providing long-term follow up on the Investigational Devices.

4.6 Poolability Analyses

The poolability across sites will be verified for the safety endpoint, percent of patients experiencing a false positive event within 12 months, and for the effectiveness endpoint, sensitivity of the ST Monitoring Feature to detect clinical events. Since it is likely that sites will have a wide variation in the number of patients enrolled (due to differences in site start-up times and differences in patient volumes at the sites), for the purpose of testing poolability, they will be classified into the following categories:

To evaluate poolability across sites, separate generalized linear models will be used for the safety and efficacy endpoints, as follows:

$$\log\left(\frac{p}{1-p}\right) = \text{site category},$$

where p is the expected proportion of patients experiencing a false positive event within 12 months (safety) or the sensitivity of the ST Monitoring Feature (efficacy). Testing will be conducted at a significance level of 15%. Poolability will be verified for an endpoint if the site category effect is not significant at the 15% significance level.

4.7 Additional Analyses

The following additional data will be collected during the study:

- Demographic variables include: gender, age, ethnicity, cardiomyopathy classification, complete cardiovascular history, arrhythmia history, primary ICD indication, and EF% at the time of enrollment and QRS duration at baseline
- ST Diagnostic Data to include: heart rate at onset of the Type I ST episode, maximum ST shift during the Type I ST episode, Type I ST episode duration, total number of Type I ST episodes detected
- All diagnostic procedures (tests and interventions) stratified by investigator's assessment of whether the procedure would have been performed in presence and absence of ST diagnostic data

Statistical Analysis Plan

- Positive Predictive Value (PPV) of the ST Monitoring Feature
- Negative Predictive Value (NPV) of the ST Monitoring Feature
- Response rates to Patient Notifier and Merlin.net Type I ST Episode detections
- Cardiac medications (including anti-anginal medications) during clinical events
- CPK Isoenzymes, MB fractions and Troponin values collected during clinical events
- Stress test and 12-lead ECG measurements collected during clinical events
- Proportion of patients who have the ST Monitoring Feature turned off at every study visit from the Programming Visit onwards
- Adverse events
- Clinical events
- Spontaneous arrhythmic episodes
- Hospitalizations
- Mortality/Death

4.7.1 Demographic Variables

Demographic variables will be collected for all patients at the time of enrollment and summaries presented. Continuous variables will be presented as mean \pm SD, and categorical variables will be tabulated with percentages.

4.7.2 ST Diagnostic Data

ST diagnostic data will be collected and presented for all Type I ST episodes for all patients with the Fortify[®] ST (upgraded), Fortify Assura[®] ST and Ellipse[®] ST devices. Additionally, ST diagnostic data from all patients with the Fortify[®] ST prior to being upgraded will be collected and presented.

4.7.3 Investigator's Assessment of Procedures Performed

All diagnostic procedures (tests and interventions) stratified by investigator's assessment of whether the procedure would have been performed in presence and absence of ST diagnostic data

4.7.4 Positive Predictive Value (PPV)

The PPV will be calculated as the proportion of true positives (according to section 3.2.3) to the number of all Type I ST episodes (i.e., combination of all true positive and false positive events).

$$PPV = \frac{TP}{TP + FP}$$

4.7.5 Negative Predictive Value (NPV)

The NPV will be calculated as the proportion of true negatives to the combination of false negatives and true negatives (according to section 3.2.3)

$$NPV = \frac{TN}{FN + TN}$$

4.7.6 Response Rates to Patient Notifier and Merlin.net Type I ST Episode Detections

The response rates to Type I ST Episode notifications received through the Patient Notifier and through Merlin.net will be presented.

4.7.7 Cardiac and Anti-Anginal Medications

List of concomitant cardiac and anti-anginal medications will be collected at the Screening visit, Baseline visit and at each clinical event and will be summarized for all patients.

4.7.8 CPK Isoenzymes MB Fractions and Troponin

Cardiac biomarker laboratory tests will be collected during any clinical event as defined by the study protocol. Results will be determined as positive or negative and will be compared to clinical events and to Type I ST episodes.

4.7.9 12-Lead ECG Measurements

12-lead ECG recordings will be collected at the Baseline visit and during any clinically-indicated stress test related to Clinical Events. Results from the 12-lead ECG recordings along with the patient's pertinent medical records will be adjudicated by the CEC and classified as normal or abnormal. All ECG abnormalities will be classified as a preexisting abnormality or as a new finding. An abnormal 12-Lead ECG is defined as having at least one of the following present 1) rhythm other than normal sinus rhythm or sinus tachycardia such as atrial fibrillation, atrial flutter, supraventricular tachycardia, ventricular tachycardia, or idioventricular rhythm 2) intermittent or complete conduction abnormalities resulting in widening of the QRS complex (RBBB, LBBB, IVCD, evidence of left ventricular hypertrophy), 3) ST-T wave abnormalities (T wave inversions, J point elevation) 4) frequent PVCs 5) low voltage QRS complexes indicative of dilated cardiomyopathy or COPD, or 6) high voltage QRS complexes indicative of left ventricular hypertrophy. A normal 12-Lead ECG will be defined as one not meeting the criteria for an abnormal ECG.

Results of any stress tests performed will be determined as positive or negative by the site and will be sent to the CEC for further adjudication

4.7.10 Adverse Events

All adverse events will be categorized by the investigator as instructed in Section 6.0 of the investigational protocol. Adverse event evaluation will include the number of patients who experienced any events, the number of events and each event classification.

4.7.11 Clinical Events

Clinical events will be summarized for all patients in terms of the number of events and number of patients. The rate of clinical events will be reported per patient-year of follow-up along with a 95% confidence interval using Ulm's method.

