3.2.2 Clinical Events

ACS Events

An ACS event is defined as any of the following:

- Death due to a myocardial infarction
- A new Q-wave myocardial infarction on 12-lead ECG
- ST elevation myocardial infarction
- Biomarker evidence of acute myocardial damage*
- Evidence of new plaque rupture by invasive testing (i.e., IVUS) as adjudicated by the blinded Clinical Events Committee
- The presence of TIMI myocardial perfusion grade 0 or 1 consistent with acute injury of the myocardium from embolization
- New surface ECG ST depression or elevation treated with thrombolytic medication

Statistical Analysis Plan

- New surface ECG ST depression or elevation with new or progressive flow-limiting ischemia proven by non-invasive or invasive testing.
- Angiographic stenosis $\geq 70\%$ adjudicated by the blinded Clinical Events Committee as flow-limiting.
- An event that leads to a clinically warranted percutaneous coronary intervention (PCI) or revascularization as determined by the blinded Clinical Events Committee. Clinically warranted is defined as:
 - Angiographically visualized stenosis $\geq 70\%$ correlating with the vascular distribution in which a 12-lead surface ECG documents changes consistent with ischemia or injury in 2 or more contiguous leads
 - Angiographically visualized stenosis $\geq 70\%$ correlating with a vascular distribution shown to have ongoing ischemia by non-invasive stress testing
 - New or progressive angiographically visualized stenosis $\geq 70\%$ correlated with new or progressive anginal symptoms

*NOTE: It is recommended that the “Universal Definition of Myocardial Infarction” proposed by the Joint ESC/ACCF/AHA/WHF in 2007 be used to determine myocardial damage.

Precursor Events

A precursor event is defined as clinical symptoms of an impending ACS event followed by an ACS event within 10 days. Precursor events alone do not meet the ACS event criteria. Multiple precursor events may precede a single ACS. All precursor events will be adjudicated by the Clinical Event Committee (CEC). Symptoms identified as precursors will be grouped with the subsequent ACS event and counted as a single event. Individual precursor events will not be included in the statistical endpoint analysis.

Non Events

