- Formation of hematomas or cysts
- Infection
- Myocardial infarction
- Peripheral nerve injury
- Pneumothorax
- Pseudo-aneurysm
- Stent thrombosis
- Stroke
- Thromboemboli
- Venous occlusion
- Venous or cardiac perforation

Analysis

- A Kaplan-Meier estimate of the proportion of patients free from complications arising from a false positive event through the 6 month follow-up visit will be provided with a 95% lower bound on the estimate using Greenwood's formula for the variance of the Kaplan-Meier estimator. If no events have been observed, then a Clopper-Pearson 95% exact lower confidence bound for the proportion of patients free from complications due to unnecessary procedures resulting from false positive events will be provided.
- A tabular presentation of ER visits, doctor office visits, or any medical care will be presented, stratified by false positive, true positive and false negative events.
- The proportion of patients with false positive events, with the count of false positive, true positive and false negative events will be provided. A preliminary estimate of sensitivity will be calculated.
- The proportion of patients with the ST monitoring feature turned off after the Programming and Baseline visits will be tabulated along with the reason for the turning off the ST monitoring feature.
- Baseline demographics and site enrollment will be tabulated.

Statistical Analysis Plan

The above analyses will be presented overall and by the following subgroups:

- Coronary artery disease patients with cardiomyopathy
- Coronary artery disease patients without cardiomyopathy
- Patients with abnormal baseline ECGs, for each of six abnormal subgroup categories
- Patients with normal baseline ECGs
- Patients with arrhythmias
- Gender
- Patients alerted via Merlin.net and patients alerted via device Patient Notifier

Additional Analysis

An analysis will be performed that includes all clinical events using a GEE logit-link linear model to estimate the sensitivity with a working correlation that provides a robust estimator of the variance adjusting for multiple clinical events within patients.

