The analysis will be carried out where only those false positives counted toward meeting the requirement of number of false positives are included. That is, if a patient has experienced more than two false positives, only the first two false positives of that patient will be included.

The 97.5% upper confidence limit for the expected FPR will be calculated based on the confidence interval calculation of a Poisson rate using the exact method (Ulm, 1990)⁶. The null hypothesis will be rejected at the 2.5% significance level if the 97.5% upper confidence limit is less than 1.9 per patient-year.

Additional Analyses

Empirical analyses will be provided for the false positive rate using

1. the estimator described in the Primary Analysis section, and
2. the estimator that uses all false positive events.

The standard error of these empirical estimators will be calculated as the standard deviation of their bootstrap distributions. The bootstrap distributions will be

Statistical Analysis Plan

constructed using 1,000 bootstrap resamples. Each bootstrap resample will be performed at the patient level (in order to preserve the correlation structure between events with a given patient), and each resample will have a total sample size equal to the total number of evaluable patients. The bootstrap distributions will be used to estimate two-sided 95% bootstrap confidence intervals.

Subgroup Analysis

The analysis of the secondary safety endpoint will be performed on the following subgroups of patients

- Coronary artery disease patients with cardiomyopathy
- Coronary artery disease patients without cardiomyopathy
- Patients with abnormal baseline ECGs, for each of six abnormal subgroup categories
- Patients with normal baseline ECGs
- Patients with arrhythmias
- Gender
- Patients alerted via Merlin.net and patients alerted via device Patient Notifier

[figure not shown]
Sample Size

[REDACTED]

[REDACTED]

[REDACTED]

[REDACTED]

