An empirical analysis will be provided for the sensitivity of the ST Monitoring Feature to detect clinical events using the estimator described in the Primary Analysis section. The standard error of this empirical estimate will be calculated as the standard deviation of a bootstrap distribution. The bootstrap distribution will be constructed using 1,000 bootstrap resamples. Each bootstrap resample will be performed at the patient level (in order to preserve the correlation structure of multiple events within one patient, if the occurs), and each resample will have a total sample size equal to the total number of evaluable patients. A two-sided 95% bootstrap confidence interval will be provided.

Subgroup Analysis

The analysis of the primary efficacy endpoint will be performed on the following subgroups of patients

- Coronary artery disease patients with cardiomyopathy
- Coronary artery disease patients without cardiomyopathy
- Patients with abnormal baseline ECGs, for each of six abnormal subgroup categories
- Patients with normal baseline ECGs
- Patients with arrhythmias
- Gender
- Patients alerted via Merlin.net and patients alerted via device Patient Notifier

Sample Size

[REDACTED]

The patients to be enrolled in the Analyze ST IDE Study are similar to those

[REDACTED]

the total number of patients required to be enrolled is 5,228.

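### The 95% interval for the clinical event rate in 4.7.11 treats events as independent, and will be too narrow if repeat events within patients are more than rare

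*Protocol*

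**What the plan says.** Section 4.7.11 states: "Clinical events will be summarized for all patients in terms of the number of events and number of patients". It then gives the rate per patient-year "along with a 95% confidence interval using Ulm's method". Section 4.3.3 describes the same method as the "confidence interval calculation of a Poisson rate using the exact method (Ulm, 1990". The Protocol and SAP texts agree.

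The events in question are broad. Under 3.2.1 the committee must "Classify clinical events as either an Acute Coronary Syndrome (ACS) Event, a Precursor Event, or a Non Event". Section 3.2.2 notes that "Multiple precursor events may precede a single ACS", and then groups precursor symptoms with the ACS event that follows and counts them once. No such grouping is stated for repeat ACS events or for Non Events.

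Elsewhere the plan allows for several events in one patient:
- Section 4.3.1 estimates sensitivity by GEE with a "robust estimator of the variance adjusting for multiple clinical events within patients".
- Section 4.4.1 adds a bootstrap for sensitivity: "Each bootstrap resample will be performed at the patient level (in order to preserve the correlation structure of multiple events within one patient".
- Section 4.3.3 limits false positives to two per patient and one per follow-up period. It adds a patient-level bootstrap "in order to preserve the correlation structure between events with a given patient".

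None of these provisions is carried into 4.7.11.

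**The concern.** An exact Poisson interval takes the variance of the event count to equal its mean. If some patients have more than one event, the count varies more than that, and the interval understates the uncertainty. Section 4.7.11 counts events as well as patients and sets no per-patient cap, so repeats enter the rate in full. The plan provides for within-patient correlation in sensitivity and in the false positive rate, but not here.

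What is at stake is how far the stated 95% can be trusted for the event rate in this population. Anyone using that rate as background for the sensitivity result, or to plan a later study, would take the interval at face value.

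**Working it through.** The plan gives no rate, event count or interval in 4.7.11, so there is no figure of its own to reproduce. The check asks how a nominal 95% Poisson interval behaves when events repeat within patients.

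**Inputs from the documents.** At least 41 clinical events at the data cut-off (3.1 in both documents; Protocol 4.5); 5,228 patients; 12 months of follow-up.

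**Assumptions.**
- 5,228 patient-years of follow-up, which ignores attrition and is for illustration only.
- 200 and 500 events as alternatives to 41, because clinical events include Non Events and the total may well exceed 41.
- All repeat-event shares.

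**Step 1: the interval as planned.** For D events the exact limits are χ²(0.025; 2D)/2 and χ²(0.975; 2D+2)/2. With D = 41 these are 29.4 and 55.6 events. Dividing by 5,228 gives a rate of 0.78 per 100 patient-years, interval 0.56 to 1.06.

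**Step 2: variance inflation.** Let m be the number of events in a patient who has any. If such patients arise as a Poisson process, the variance of the total is φ times its mean, with φ = E[m²]/E[m].
- If a share q has exactly two events and the rest one, φ = (1+3q)/(1+q). For q = 0.10 this is 1.30/1.10 = 1.182; for q = 0.20 it is 1.60/1.20 = 1.333.
- If each event is followed by another with probability r (geometric recurrence), φ = (1+r)/(1−r). For r = 0.4 this is 1.4/0.6 = 2.333.

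The true standard error is √φ times the Poisson one.

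**Step 3: coverage of the nominal 95% Poisson interval** (200,000 simulated trials per row and event count).

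| Assumed repeats among affected patients | φ | SE ratio | 41 events | 200 events | 500 events |
|---|---|---|---|---|---|
| None | 1.000 | 1.00 | 95.8% | 95.2% | 95.1% |
| 5% have two | 1.095 | 1.05 | 94.9% | 94.1% | 94.0% |
| 10% have two | 1.182 | 1.09 | 93.9% | 93.1% | 93.0% |
| 20% have two | 1.333 | 1.15 | 92.3% | 91.4% | 91.2% |
| 30% have two | 1.462 | 1.21 | 90.8% | 89.8% | 89.6% |
| Geometric, r = 0.2 | 1.500 | 1.22 | 90.5% | 89.4% | 89.2% |
| Geometric, r = 0.3 | 1.857 | 1.36 | 86.5% | 85.4% | 85.2% |
| Geometric, r = 0.4 | 2.333 | 1.53 | 81.7% | 80.5% | 80.2% |

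With few events the exact method is slightly conservative, which offsets mild clustering. That margin fades as events accumulate; the clustering does not.

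**Step 4: effect on the interval.** A patient-level robust interval on the log scale is D·exp(±1.96·√(φ/D)). At D = 41 over 5,228 patient-years it gives, per 100 patient-years:
- 0.57 to 1.08 with 5% having two events;
- 0.56 to 1.09 with 10%;
- 0.55 to 1.12 with 20%;
- 0.49 to 1.25 with geometric recurrence at r = 0.4.

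**Step 5: unequal patient risk alone.** If patients differ in risk (gamma frailty with variance θ) but events are otherwise unlinked, φ = 1 + μθ, where μ is the mean number of events per patient. At μ = 41/5,228 = 0.0078 and θ from 1 to 5, φ is 1.01 to 1.04, which is negligible. At μ = 500/5,228 = 0.096 it is 1.10 to 1.48.

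**The case against.** The strongest reply is that the documents do not show repeats to be common. Provision for multiple events in the GEE and bootstrap analyses shows that they are possible, not how often they occur. With 5% of affected patients having two events and 41 events in all, the planned interval keeps about 95% coverage. This stands. A reader might infer that the interval is certain to fall short of 95%, and the documents do not support that.

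Second, a reader might take the remark about several precursors per ACS event as proof that clusters enter the rate. The same paragraph of 3.2.2 counts precursors together with their ACS event as one event, which removes that source if the rule applies in 4.7.11. This stands too, but only in part: 4.7.11 does not say whether the rule applies, and it does not touch repeat ACS events or Non Events.

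Third, the false positive rate in 4.3.3 is itself tested with Ulm's interval, and its bootstrap is only an additional analysis. The lack of a bootstrap in 4.7.11 is therefore an omission rather than a contradiction. That is fair. The false positive analysis does, however, limit events per patient as well as adding the bootstrap, and the clinical event rate has neither.

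Finally, 4.7.11 belongs to the additional analyses and has no hypothesis or threshold. Because it reports both events and patients, a reader could see the average number of events per affected patient. Both points are correct and limit the importance of the matter, but the printed interval would still carry no allowance for clustering.

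**Conclusion.** The point holds conditionally: 4.7.11 applies an independence-based interval to events that may repeat within a patient, and that interval will be too narrow if repeats are more than rare. With 41 events, the loss of coverage runs from practically none (5% of affected patients with two events) to about four percentage points (30%). Geometric recurrence of 0.3 to 0.4 would bring coverage down to 86.5% to 81.7%. With 200 to 500 events, coverage is about 93% at 10% and 91% at 20%. All repeat shares, the larger event counts and the patient-years are assumptions, because the documents give no repeat frequency.

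A reader might also infer that the primary or secondary endpoint conclusions are affected. They are not: no endpoint test uses this interval. This is a small improvement to a descriptive result.

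**What to change.** In 4.7.11, compute the 95% interval with the patient-level bootstrap already specified in 4.3.3 (1,000 resamples), drawing each patient with all of their events and follow-up time. A rate model with robust variance clustered on the patient would also do. Keep Ulm's interval only as a supplement, or for use when there are too few events to bootstrap. State in the same section that precursors grouped with an ACS event count once, as in 3.2.2.

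This takes a sentence or two in the plan. The method is already specified, so the cost is slightly more analysis work and possibly a slightly wider interval. If repeats prove rare, the result will hardly change.
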